10.4.5 ADHERENCE AND RETENTION ANALYSES

Adherence to the protocol will be assessed by calculating the number (%) subjects' data for each endpoint assessment that is not provided in subjects Case Report Forms. This will be further analyzed as per frequency of each endpoint data that is not available due to loss to follow-up, discontinuation of the intervention or any other reason.

10.4.6 BASELINE DESCRIPTIVE STATISTICS

Subjects baseline scores of all endpoints (GAIS, MSS and POSAS) will be compared using descriptive statistics such as mean score, standard deviation, standard error, range and graphical presentations.

10.4.7 PLANNED INTERIM ANALYSES

Not applicable. There will be no interim analysis during this study.

10.4.7.1 SAFETY REVIEW

There will be no interim analysis during this study. However, this study may be suspended or prematurely terminated if there is sufficient reasonable cause as per section 5.5 and 8.5.

10.4.7.2 PERFORMANCE REVIEW

There will be no interim analysis during this study. However, this study may be suspended or prematurely terminated if there is sufficient reasonable cause as per section 5.5 and 8.5.

10.4.8 ADDITIONAL SUB-GROUP ANALYSES

Not applicable. Primary or secondary endpoints will not be analyzed based on age, sex, race/ethnicity or other demographic characteristic(s).

10.4.9 MULTIPLE COMPARISON/MULTIPLICITY

Not applicable.

10.4.10 TABULATION OF INDIVIDUAL RESPONSE DATA

Individual participant data will be listed by measure and time point as appendix to the study report.

10.4.11 EXPLORATORY ANALYSES

Not applicable.

10.5 SAMPLE SIZE

One of the primary performance endpoints outcome measures was used to calculate the study sample size.

Sample size calculation using the subject's improvement of surgical scars at 3 months post-treatment as evaluated by independent blinded reviewer using the General Aesthetic Improvement Scale (GAIS);

- Null and alternate hypotheses:
 - **Null Hypothesis ($H_0: \mu_d = \mu_{post} - \mu_{pre} = 0$)** – There is no improvement of surgical scars at 3 months post-treatment review compared to baseline.
 - **Alternative Hypothesis ($H_a: \mu_d = \mu_{post} - \mu_{pre} \neq 0$)** – There is improvement of surgical scars at 3 months post-treatment review compared to baseline. The improvement of surgical scars will be defined by General Aesthetic Improvement Scale (GAIS) scores evaluated by independent blinded reviewer. Expected mean improvement difference is not less than one (1) GAIS score higher than baseline.
- In view of the nature of this study in regard to treatment period of 3 months and up to 10 months follow-up, we make provision for 30% study drop out, withdrawal or loss to follow-up.
- Due to the natures of 3 types of surgical scars that will be treated in this clinical study, the study will be viewed as 3 groups of cohort studies;
 - breast augmentation cohort group
 - abdominoplasty cohort group
 - face lift cohort groupThe study's sample size calculation below is number of subjects required for each group the makes up the study
- 2-Tailed Sample Size calculation formula for Matched Samples was used in the table below:

(1- β), Power	0.9
α , Level of Significance	0.05
μ_d , mean difference; this is the expected improvement (difference) to treatment assessed by GAIS scores under H_a	1.0
σ_d , Standard Deviation of the difference scores (GAIS range $\div 4$) = [4 \div 4]	1.0
ES, Effect Size $[(\mu_d/\sigma_d)]$	1.0
$Z_{1-\alpha/2}$	1.96
$Z_{1-\beta}$, (for 90%)	0.84
Estimated Sample Size	10.51 \approx 11
Estimated Sample Size + 30% drop out	14.30 \approx 15

Conclusion: The estimated sample size for each cohort group obtained from the primary performance endpoint outcome measure calculation plus 30% drop out provision that will be used for this study is 15.

The study will enroll up to 50 female subjects requesting treatment of surgical scars following breast augmentation or abdominoplasty and up to 25 male and female subjects requesting treatment of surgical scars following face lift surgery.

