10.2 STATISTICAL HYPOTHESES

The null and alternative hypotheses for the study's primary, key secondary and safety endpoints are;

- Primary Performance Endpoint:
 - **Null Hypothesis ($H_0: \mu_d = \mu_{post} - \mu_{pre} = 0$)** – There is no improvement of surgical scars at 3 months post-treatment review compared to baseline.
Alternative Hypothesis ($H_a: \mu_d = \mu_{post} - \mu_{pre} \neq 0$) – There is improvement of surgical scars at 3 months post-treatment review compared to baseline. The improvement of surgical scars will be defined by General Aesthetic Improvement Scale (GAIS) and Manchester Scar Scale (MSS) scores evaluated by independent blinded reviewer. Expected mean improvement difference is not less than one (1) GAIS and MSS score higher than baseline.
 - **Null Hypothesis ($H_0: \mu_d = \mu_{post} - \mu_{pre} = 0$)** – There is no improvement of surgical scars at 10 months post-treatment review compared to baseline.

Alternative Hypothesis ($H_a: \mu_d = \mu_{post} - \mu_{pre} \neq 0$) – There is improvement of surgical scars at 10 months post-treatment review compared to baseline. The improvement of surgical scars will be defined using General Aesthetic Improvement Scale (GAIS) and Manchester Scar Scale (MSS) scores evaluated by independent blinded reviewer. Expected mean improvement difference is not less than one (1) GAIS and MSS score higher than baseline.

- Secondary Performance Endpoint(s):
 - **Null Hypothesis ($H_0: \mu_d = \mu_{post} - \mu_{pre} = 0$)** – There is no improvement of surgical scars at 1 and 2 months post-treatment review compared to baseline.
Alternative Hypothesis ($H_a: \mu_d = \mu_{post} - \mu_{pre} \neq 0$) – There is improvement of surgical scars at 1 and 2 months post-treatment review compared to baseline. The improvement of surgical scars will be defined using General Aesthetic Improvement Scale (GAIS) and Manchester Scar Scale scores evaluated by independent blinded reviewer.
 - **Null Hypothesis ($H_0: \mu_d = \mu_{post} - \mu_{pre} = 0$)** – There is no improvement of surgical scars at 3 and 10 months post-treatment review compared to baseline.
Alternative Hypothesis ($H_a: \mu_d = \mu_{post} - \mu_{pre} \neq 0$) – There is improvement of surgical scars at 3 and 10 months post-treatment review compared to baseline. The improvement of surgical scars will be defined using Patient and Observer Scar Assessment Scale (POSAS) scores evaluated by independent blinded reviewer.

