10.3 ANALYSIS DATASETS

Modified Intention-to-Treat Analysis Dataset will be used; performance and safety analyses will be carried out on all subjects who received at least one treatment of Venus Viva™ system and for whom at least one valid post-baseline performance and safety evaluation were obtained.

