10.4.2 ANALYSIS OF THE PRIMARY PERFORMANCE ENDPOINT(S)

The following will be considered for the analysis primary performance endpoint:

Summary table for differences of baseline, 3-month and 10-month post treatment General Aesthetic Improvement Scale (GAIS) and Manchester Scar Scale (MSS) scores will be displayed as mean difference, standard deviation and standard error. The General Aesthetic Improvement Scale (GAIS) scores is a 5-point scale improvement assessment chart while Manchester Scar Scale (MSS) is two scales whose scores are combined - an overall VAS and seven scar parameters.

Bar, pie charts or graphs indicating scores will also be used to analyse performance, where applicable.

All statistical tests will be two-sided. The level of statistical significance for effectiveness analyses is 5% ($\alpha = 0.05$) for all tests of differences. Where appropriate, Paired t-test and/or Wilcoxon Signed-Ranks Test for Matched Pairs will be used to compare the evaluations of General Aesthetic Improvement Scale (GAIS) scores and Manchester Scar Scale (MSS) scores at 3 and 10 months against baseline. Analysis of Covariance (ANCOVA) may also be used where appropriate.

The Paired t-test and/or Wilcoxon Signed-Ranks Test for Matched Pairs will enable us to accept or reject the null hypotheses. Rejection of null hypotheses will establish that:

- The two-sided 95% confidence interval for the difference between the means excludes zero.
- The two means are statistically significantly different at the 5% level ($P < 0.05$) two-sided.

Upon rejection of null hypotheses, further statistical test tools such as Confidence Interval and/or t-test will be used to test expected primary performance endpoint; that is alternative hypothesis that $H_a \geq 1$. This will be used to determine if the study meets the primary performance endpoint.

General Aesthetic Improvement Scale (GAIS) scores and Manchester Scar Scale (MSS) scores of all subjects who received at least one treatment of Venus Viva™ system for the treatment of surgical scars following breast augmentation, abdominoplasty or face lift and for whom at least one valid post-baseline GAIS and MSS assessment were obtained will be analysed for the primary endpoint. Multiple imputation method or modelling of available data may be used for missing data as appropriate.

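### The sections conflict on whether the primary analysis is by cohort or pooled, no rule combines the four primary comparisons or defines the ≥ 1 step, and at 15 enrolled with 30% loss the per-cohort t-test has 80–85% power, not 90%

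*Combined protocol and SAP*

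**What the plan says.** **Sizing.** Section 10.5 states that, because three types of scar are treated, "the study will be viewed as 3 groups of cohort studies": breast augmentation, abdominoplasty and face lift. It adds that the "sample size calculation below is number of subjects required for each group". The table gives 90% power, two-sided 5%, mean GAIS difference 1.0, SD 1.0 (range 4 divided by 4), a z for power printed as 0.84, and 10.51, rounded to 11. The conclusion is that the estimate for each cohort "plus 30% drop out provision that will be used for this study is 15". On recruitment: "The study will enroll up to 50 female subjects requesting treatment of surgical scars following breast augmentation or abdominoplasty", with up to 25 more for face lift. The 50 is not divided between its two cohorts.

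**Analysis.** Section 10.2 gives the hypotheses once, with no cohort term. Section 10.3 says "performance and safety analyses will be carried out on all subjects who received at least one treatment". Section 10.4.2 uses a paired t-test and/or Wilcoxon signed-rank test on GAIS and "Manchester Scar Scale (MSS) scores at 3 and 10 months against baseline", each at two-sided 5%, on all treated subjects with a valid post-baseline score. Section 10.4.8 rules out demographic subgroup analyses and is silent on scar type. Section 10.4.9 marks multiplicity as not applicable.

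**Decision.** Section 10.2 expects: "Expected mean improvement difference is not less than one (1) GAIS and MSS score higher than baseline". Section 10.4.2 says that once zero is rejected, a confidence interval and/or t-test will be used on the alternative of a difference of at least 1, and "This will be used to determine if the study meets the primary performance endpoint".

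**The concern.** The plan's power statement belongs to three by-cohort tests, while its analysis sections describe one undivided set. A reader of the results could not tell whether the primary endpoint was met, or for which scar type.

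Two further gaps compound this. With two scales and two time points there are four primary comparisons, and nothing says whether one, some or all must succeed. The step that settles success, a difference of at least 1, has no pass criterion, and the sample size was not calculated for it. Different reasonable readings of the same text therefore give different error rates, different power and possibly different conclusions.

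**Working it through.** Differences are taken against baseline, as in 10.2 and 10.4.2.

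**1. The plan's own figure.** For paired data, n = (z₁₋α/₂ + z₁₋β)² / ES². With ES = 1, two-sided 5% and z = 1.2816 for 90% power, n = (1.960 + 1.2816)² = 10.51, rounded to 11. This reproduces. The printed 0.84 is the 80% value and would give (1.96 + 0.84)² = 7.84, rounded to 8. The result was therefore computed with 1.28, and the table entry is a misprint.

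**2. Evaluable per cohort.** The plan inflates 11 × 1.3 = 14.3, rounded to 15. After 30% loss, 15 × 0.7 = 10.5, so 10 or 11 remain. Dividing instead, 11 / 0.7 = 15.7, gives 16.

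**3. Per-cohort power at effect size 1, two-sided 5%** (t-test from the noncentral t with n − 1 df):

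| Evaluable | Normal formula | Paired t-test |
|---|---|---|
| 10 | 88.5% | 80.3% |
| 11 | 91.3% | 84.8% |
| 12 | 93.4% | 88.3% |
| 13 | 95.0% | 91.1% |
| 17 | 98.5% | 97.2% |

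The Wilcoxon test, by simulation with normal differences, gives about 78% at 10 and 81% at 11. Most of the shortfall comes from using a normal formula at so small an n. At 5%/3 per cohort, t-test power is 60.4% at 10, 67.1% at 11 and 91.1% at 17.

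**4. Pooled power.** Three cohorts of 15 give 45 × 0.7 = 31.5, so 31 evaluable. With scar type as a factor (28 df), power is over 99.9% at effect size 1 and 90% at 0.6.

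**5. Error over the four comparisons if rejecting zero were enough.**
- Any one of four, pooled: 1 − 0.95⁴ = 18.5% if independent.
- Any one of 12 (three cohorts × four): 1 − 0.95¹² = 46.0% if independent.
- Both scales at either time point, pooled: at most 2 × 5% = 10%.
- All four: at most 5% (within each cohort, if run by cohort).

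An assumed positive correlation among the four comparisons lowers the first two: to 11–17% and 30–44% at correlations of 0.8–0.3.

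**6. The ≥ 1 step at the plan's assumptions (true mean 1, SD 1).**
- Lower 95% bound must exceed 1: passes 2.5% of the time at any n, by construction.
- Zero rejected and estimate at least 1: 49.6% at n = 10 and 50.0% at n = 17, because the estimate falls above its true value half the time.

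The stated power therefore applies only to the test against zero.

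**7. Error at a true mean of zero under the second form, comparisons independent.**
- By cohort, n = 10: per test 0.08% at SD 1 and 2.1% at SD 2. Over 12 tests, 1 − (1 − 0.0008)¹² ≈ 1% and 1 − (1 − 0.021)¹² ≈ 22–23%.
- Pooled, n = 31, any of four: about 0% at SD 1 and about 1% at SD 2.

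SD 2 is illustrative, since the plan gives no SD for MSS.

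**The case against.** **Power.** The 80–85% holds only at 15 enrolled with the full 30% loss. That loss is provided for follow-up to 10 months, whereas the sized endpoint is at 3 months; 13 evaluable of 15 would give 91%. Section 10.4.2 admits anyone with a valid post-baseline score and allows multiple imputation. The caps would allow 25 per cohort, giving 17 evaluable and 97%. All this is correct, but the 30% is the plan's own provision, the caps are ceilings, and no minimum above 15 is stated for any cohort. If the analysis is pooled, power is ample and the shortfall has no consequence; the plan does not say that it is. The optional ANCOVA does not settle this, since the covariates named in 10.4.1 are baseline scores, not scar type.

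**Error rates.** A reader might infer a false-positive rate of 18.5% or 46%. The documents do not support that as the trial's error rate. Section 10.4.2 makes rejection of zero only a first step, and the ≥ 1 step then decides; with it, the error can be far lower. The wording of 10.2 can also be read as needing both scales. What stands is that no rule is written, so no single rate applies.

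**Printed z.** A reader might infer from 0.84 that the trial was sized for 80% power. It was not: 10.51 needs 1.28.

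**Blinding.** A reader might infer that an unblinded analyst will choose the rule after seeing results. Section 10.6.2 does say the biostatistician is not blinded, but in wording about a party conducting interim analysis, and 10.4.7 plans none. Section 10.1 also places any revised SAP before database lock and unblinding. The point does not rest on this.

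**Conclusion.** The concern holds as a conflict between sections, together with missing decision rules. Section 10.5 sizes three cohorts; 10.2, 10.3 and 10.4.2 describe one analysis of all treated subjects. The plan contains both views of the unit and does not choose.

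If the unit is the cohort, the stated 90% is really 80–85% for the planned t-test. This assumes effect size 1, 15 enrolled and 30% loss, and the SD of 1 is itself only a range-based guess. If the unit is the pooled set, power exceeds 99.9% at the same effect size.

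The missing rules matter more than the power gap. Depending on the reading, the error for rejecting zero runs from at most 5% to 18.5% pooled, or 46% over 12 by-cohort tests. The decisive ≥ 1 step passes 2.5% or about 50% of the time at the plan's own assumptions. These figures show how far the readings diverge; none is the trial's established error rate or power.

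**What to change.** Before any reviewer score is released:

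1. **Name one primary analysis unit in 10.4.2 and reconcile 10.5 with it.**
   - (A) Pooled, with scar type as a factor and cohort estimates with 95% CI as descriptive. State pooled power: 31 evaluable, over 99.9% at effect size 1 and 90% at 0.6.
   - (B) By cohort. If each cohort is tested at 5% as a separate study, restate power as about 80–85% at 15 enrolled; 19 enrolled each (19 × 0.7 = 13.3, so 13 evaluable) gives 91%. If alpha is split at 5%/3, restate it as about 60–67% at 15 enrolled; 25 enrolled each (17 evaluable) gives 91%. State a minimum enrolment for each cohort.
2. **Correct the printed z** for 90% power in 10.5.
3. **Replace the entry in 10.4.9** with one rule over the four comparisons, for example a fixed sequence at the chosen alpha, or all four required. If all four are required by cohort at 5%, power at 15 enrolled is about 42–52% with independent comparisons (0.803⁴ to 0.848⁴, assuming effect size 1 for each), and higher if they are positively correlated.
4. **Settle the ≥ 1 step.** Make it descriptive (estimate and 95% CI set against 1), or give it an exact pass rule with its power and an SD for MSS.

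**Cost.** Section 10 is part of the protocol, so this is an amendment needing ethics committee approval (13.2, 14.3); detail can go in the formal SAP that 10.1 allows. No option needs more than the caps: 19 + 19 = 38 or 25 + 25 = 50 against 50, and 19 or 25 against 25. Under a fixed sequence, later endpoints cannot be claimed if an earlier one fails. Under B at 15 enrolled, the stated power becomes less favourable. Under A, scar-type results are descriptive only.

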I will conduct the trial in accordance with the clinical investigation plan, Good Clinical Practice guidelines, ISO 14155:2011 (Clinical Investigation of Medical Devices for Human Subjects - Good Clinical Practice), as well as local regulations. I also accept respective revisions to the clinical investigation plan approved by authorized personnel of the Sponsor and by regulatory authorities.

Institution:

[name] [name]

Principal Investigator (Printed name)

Principal Investigator (Signature)

22/2/18

Date

PROTOCOL SUMMARY

TITLE	Clinical Evaluation of the Safety and Performance of Fractional RF for the Treatment of Surgical Scars Following Breast Augmentation, Abdominoplasty or Face Lift
SUMMARY	Split-body/face evaluator-blind study of the safety and performance of fractional RF for the treatment of surgical scars following breast augmentation, abdominoplasty or face lift. The study will enroll up to 50 female subjects requesting treatment of surgical scars following breast augmentation or abdominoplasty and up to 25 male and female subjects requesting treatment of surgical scars following face lift surgery. Subjects will receive a total of three treatments of their surgical scars at one-month intervals on one side of the body or facial incision only. Subjects will be followed up at one, two, three and ten months after their last treatment. Analysis will be performed on all subjects who receive at least one treatment. Outcomes will be compared to the non-treated side.
OBJECTIVES	The objective of this clinical study is to evaluate the safety and performance of fractional RF for the treatment of surgical scars following breast augmentation, abdominoplasty or face lift.

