10.4 DESCRIPTION OF STATISTICAL METHODS

10.4.1 GENERAL APPROACH

All summary tables for quantitative parameters will display mean, standard deviation, median, range (minimum and maximum), percentages as well as number of missing data (if relevant). All summary tables for qualitative parameters will display counts, percentages and number of missing data if relevant. Baseline data are defined as the last measurement performed before the first treatment on Visit 2.

All statistical tests will be two-sided. The level of statistical significance for effectiveness analyses is 5% ($\alpha = 0.05$) for all tests of differences. Where appropriate, Paired t-test and/or Wilcoxon Signed-Ranks Test for Matched Pairs will be used to compare the evaluations at the baseline and post treatment sessions. This test will enable us to accept or reject the null hypotheses. Rejection of null hypotheses will establish that:

- The two-sided 95% confidence interval for the difference between the means excludes zero.
- The two means are statistically significantly different at the 5% level ($P < 0.05$) two-sided.

Upon rejection of null hypotheses, further statistical test tools such as Confidence Interval and/or t-test will be used to determine the performance of Venus Viva™ fractional RF System in the treatment of surgical scars following breast augmentation, abdominoplasty or face lift.

In order to accommodate imbalances of some baseline General Aesthetic Improvement Scale (GAIS) and Manchester Scar Scale (MSS) scores, covariate adjustment analysis may be performed in SAP to estimate adjusted treatment effects for the primary endpoint analysis.

The assumption for the statistical test is that the paired differences of baseline and post treatment data are normally distributed.

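### The 90% per-cohort power in Section 10.5 is unsupported: the SD of the difference is taken from the range of one GAIS rating, which assumes a baseline-to-follow-up correlation of 0.5 if baseline GAIS is scored

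*Combined protocol and SAP*

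**What the plan says.** Section 10.5 sizes each of the three cohorts (breast augmentation, abdominoplasty, face lift) separately on GAIS at 3 months. The hypothesis is written as post minus pre, and "2-Tailed Sample Size calculation formula for Matched Samples was used in the table below". The effect is set by "Expected mean improvement difference is not less than one (1) GAIS score higher than baseline". The spread row of the table is labelled "Standard Deviation of the difference scores (GAIS range" divided by 4, worked as 4 ÷ 4 = 1.0. The result is 10.51, rounded to 11. Then "we make provision for 30% study drop out, withdrawal or loss to follow-up" takes it to 14.30, rounded to 15 per cohort.

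Other places bear on what the difference is:

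- Section 10.4.2 says of GAIS that the "scores is a 5-point scale improvement assessment chart", yet it plans paired tests of the 3- and 10-month scores against baseline.
- Section 10.4.1 allows covariate adjustment, opening with "In order to accommodate imbalances of some baseline General Aesthetic Improvement Scale (GAIS".
- Section 10.4.6 plans descriptive statistics of baseline GAIS.
- The Schedule of Events (7.3.7) marks a blinded-reviewer GAIS at Visit 2.
- The Protocol Summary adds: "Outcomes will be compared to the non-treated side".

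No section gives pilot data, a per-rating SD, or a correlation between paired ratings.

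**The concern.** The row names the SD of a difference, but the number comes from the range of one score. The two coincide only under a condition that the plan does not state. The SD of a paired difference depends on how strongly the two ratings are correlated as well as on the spread of each. The treated-versus-untreated comparison promised in the Protocol Summary is also a difference of two ratings, so it has the same gap.

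The 11, the 15 and the 90% all depend on this input. If the true SD of the difference is larger, a non-significant result in one cohort could be read as failure of the device when the test had only a moderate chance of success. No estimate is biased by this. What is at stake is the stated power and how a null cohort result is read.

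**Working it through.** **Inputs from the plan.** Mean difference 1.0; σd = 1.0; two-sided α = 0.05; power 0.90; 30% loss; paired design (Section 10.5). The analysis is a paired t-test and/or Wilcoxon signed-rank test (Section 10.4.2). **Assumption, not in the plan:** the correlation ρ between the two ratings, examined from 0.5 down to −1.

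**1. Reproduce the plan's figure.** n = (z₀.₉₇₅ + z₀.₉₀)² × (σd/μd)² = (1.96 + 1.2816)² × 1 = 10.51, so 11. This matches. The table prints 0.84 as the power quantile, but (1.96 + 0.84)² = 7.84, which would give 8, so the calculation used 1.28 and the 0.84 is a misprint. Next, 11 × 1.3 = 14.3, so 15, also as stated.

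**2. What σd = 1.0 implies.** Apply the range/4 rule to one 5-point rating: SD = 4/4 = 1. For two ratings of SD 1, σd = √(1 + 1 − 2ρ) = √(2(1 − ρ)):

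- ρ = 0.5: σd = 1.00
- ρ = 0.25: σd = √1.5 = 1.22
- ρ = 0: σd = √2 = 1.41
- ρ = −1: σd = √4 = 2.00

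The plan's value is therefore the case ρ = 0.5. A correlation above 0.5 would make σd smaller than planned (0.71 at ρ = 0.75).

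**3. Power at the planned numbers.** Mean difference 1, two-sided 0.05. The paired t figures use the noncentral t distribution with noncentrality √n/σd. The normal figure is Φ(√n/σd − 1.96). Ten completers is 15 × 0.7 = 10.5, rounded down. Seventeen is 25 × 0.7 = 17.5, rounded down, for a cohort that fills to 25, the face-lift maximum.

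| σd (ρ) | Normal, n = 11 | Paired t, n = 11 | Paired t, n = 10 | Paired t, n = 17 | Completers for 90% (paired t) |
|---|---|---|---|---|---|
| 1.00 (0.5) | 91% | 85% | 80% | 97% | 13 |
| 1.22 (0.25) | 77% | 69% | 63% | 88% | 18 |
| 1.41 (0) | 65% | 56% | 51% | 78% | 24 |
| 2.00 (−1) | 38% | 32% | 29% | 49% | 44 |

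**4. Separate the two effects.** At the plan's own σd of 1.0, the planned t-test already has 85% power with 11 completers, not 90%, because the normal formula ignores estimation of the SD. The rest of the fall down each column is due to σd.

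**The case against.** The strongest defence is that GAIS is already a measure of change. Section 10.4.2 describes it as an improvement chart, and Section 10.5 describes the mean difference as the expected improvement assessed by GAIS. If the baseline value is a constant meaning no change, post minus pre is a single rating less a constant. It then spans at most 4 points, and 4/4 is a correct use of the range rule. This reading stands as a possibility. It conflicts with the scheduled Visit 2 GAIS, the allowance for baseline GAIS imbalance and the baseline GAIS summaries. It also does not cover the comparison with the untreated side. The documents are ambiguous rather than plainly in error.

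A second objection is that 15 per cohort is not the ceiling. Up to 25 face-lift subjects may enrol, and up to 50 across the other two cohorts with no split given. With 17 completers, power is 97% at σd 1.0 and 78% at 1.41. That is a fair point and softens the consequence, but an upper limit on enrolment does not guarantee more than the 15 on which Section 10.5 concludes.

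A reader might go further: a difference of two 5-point scores runs from −4 to +4, so the same rule gives 8/4 = 2, and power is about 30% instead of 90%. The documents do not support that. Section 10.5 applies its rule to the GAIS range, not to the range of a difference. With SD 1 per rating, σd = 2 requires a correlation of −1 between two ratings of the same subject's scar, which makes it a worst case and not a planning value. The contrast also mixes methods: 90% comes from the normal formula, which gives 38% at σd = 2 and n = 11, whereas 29% to 32% is the t-test figure for 10 to 11 completers.

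**Conclusion.** The concern holds in a limited form. The value σd = 1.0 has no stated basis as the SD of a difference, so the 90% power claim for 11 completers per cohort is not supported. If baseline GAIS is scored and each rating has SD 1, the planned t-test has 85% power at 11 completers when ρ = 0.5, 69% when ρ = 0.25 and 56% when ρ = 0. The 32% at σd = 2.0 is the limit under that assumption and should not be presented as the expected power. If GAIS is instead one rating against a fixed reference, σd = 1.0 follows from the range rule, and what remains is the gap between 85% and 90% together with the sections that contradict that reading. The per-rating SD of 1 is itself only a range-based guess, and every figure assumes a true mean difference of one point.

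**What to change.** In the Section 10.5 table, do one of two things:

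- State the per-rating SD and the assumed correlation that give σd, with their source.
- State that GAIS is a single improvement rating tested against a fixed no-change value. Then bring the hypotheses in 10.2 and 10.5, the Visit 2 GAIS entry in 7.3.7, and the baseline GAIS wording in 10.4.1, 10.4.2 and 10.4.6 into line.

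In either case, replace the single 90% figure with per-cohort paired t-test power at the expected number of completers over a plausible σd range, for example 1.0 to 1.41, with 2.0 shown as the worst case. Do not write 8/4 = 2.0 in as the planning value. Do not confine the 90% claim to a pooled test with 44 completers either: that number depends on σd = 2.0, and pooling would depart from the three-cohort framing of Section 10.5.

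The cost is a rewording of the table and, on the second option, of the related sections. The correction needs no extra patients. The downside is a less favourable stated power for each cohort.

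### Section 10.5 multiplies by 1.3 where a 30% loss calls for division by 0.70 (15 per cohort instead of 16) and, separately, misprints the Z value for 90% power

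*Combined protocol and SAP*

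**What the plan says.** Section 10.5 sizes the study on the blinded reviewer's GAIS score at 3 months post-treatment and applies the result to each of three cohorts (breast augmentation, abdominoplasty, face lift). It states the method: "2-Tailed Sample Size calculation formula for Matched Samples was used in the table below". The inputs are power 0.9, two-sided alpha 0.05, a mean difference of 1.0 and a standard deviation of the differences of 1.0 (GAIS range of 4 divided by 4), so the effect size is 1.0. The Z for power is labelled as the 90% value and printed as 0.84.

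The table then gives "Estimated Sample Size 10.51", rounded to 11, and "Estimated Sample Size + 30% drop out 14.30", rounded to 15. The allowance is described in the text: "we make provision for 30% study drop out, withdrawal or loss to follow-up". The conclusion is that the "calculation plus 30% drop out provision that will be used for this study is 15". The section closes with enrolment ceilings of up to 50 for breast augmentation and abdominoplasty together and up to 25 for face lift. It gives no minimum per cohort other than the 15.

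**The concern.** The two figures need separate treatment.

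The loss allowance is meant to ensure that enough subjects remain after 30% of those enrolled are lost. Adding 30% to the number needed does not do that, because the loss applies to the larger, enrolled number. Fifteen is the only per-cohort target in the plan, so an error there goes straight into the recruitment target.

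The printed Z contradicts both the power stated in the same table and the result printed below it. Someone checking the table from its own inputs cannot reproduce it, and could doubt whether 80% or 90% power was intended.

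**Working it through.** **Inputs, all from section 10.5.** Power 0.90; two-sided alpha 0.05; mean difference 1.0; SD of differences 1.0; loss 30%; printed Z for power 0.84.

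**Step 1: reproduce the evaluable number.** The matched-sample normal formula is n = ((Z for alpha + Z for power) × SD / difference)².

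- With the 90% quantile: (1.95996 + 1.28155)² = 10.507, that is 10.51, rounded up to 11. This is the plan's figure.
- With the printed 0.84: (1.96 + 0.84)² = 7.84, rounded up to 8. This is not the plan's figure.
- One-sided variants give 6.18 (80% power) and 8.56 (90% power). Neither matches.

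The 10.51 was therefore computed for 90% power, two-sided. The 0.84 was printed but not used.

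**Step 2: reproduce the enrolled number.**

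- 11 × 1.3 = 14.30, rounded up to 15. This matches the plan exactly.
- Starting from the unrounded figure would give 10.51 × 1.3 = 13.66, so the plan multiplied the rounded 11.

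**Step 3: apply a 30% loss to those enrolled.** The number to enrol is the evaluable number divided by (1 − loss).

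- 11 / 0.70 = 15.71, rounded up to 16.
- From the unrounded figure: 10.51 / 0.70 = 15.01, which also rounds up to 16.
- 15 × 0.70 = 10.5 expected evaluable, below 11.
- 16 × 0.70 = 11.2 expected evaluable, above 11.
- Fifteen can lose 15 − 11 = 4 subjects, and 4 / 15 = 27%.

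**Step 4: cost in power by the plan's normal formula.** Power = Φ(√n − 1.96) at effect size 1.0.

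| Evaluable n | Power |
|---|---|
| 10 | 88.5% |
| 10.5 | 89.98% |
| 11 | 91.3% |

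**Step 5: room under the ceilings.** Sixteen per cohort is 2 × 16 = 32 of the 50, and 16 of the 25, or 48 in all.

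**The case against.** The strongest reply is that the shortfall is almost entirely rounding. The unrounded need is 10.51, and 15 enrolled leave 10.5 after 30% loss, which by the same formula is 89.98% power. That is correct and is why the point is minor. It does not make 15 right: the plan itself rounds up to 11, and dividing either 11 or 10.51 by 0.70 and rounding up gives 16.

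Three features of the plan soften the effect further:

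- **Ceilings.** They allow more than 15 per cohort; a cohort of 25 would keep 17.5 after 30% loss. But they are upper limits, and the split of the 50 between two cohorts is not fixed, so no cohort is assured of 16.
- **Analysis set.** Section 10.3 keeps treated subjects who have at least one valid post-baseline evaluation, and section 10.4.2 permits multiple imputation, so some who leave early may still contribute.
- **Timing.** The 30% is justified by the full treatment and follow-up period, while the sizing endpoint is at 3 months post-treatment. Loss by then may be lower.

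These bear on how much the error matters. None turns 15 into the number that a 30% allowance requires.

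A fair limitation also stands: restoring 11 evaluable does not settle the power of the planned analysis. Section 10.4.2 names a paired t-test and/or Wilcoxon test. An exact paired t-test at effect size 1.0 has 84.8% power at 11 and needs 13 evaluable for 90%. That gap is larger than the one described here and comes from the normal approximation, not from the loss allowance.

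A reader might also infer from the 0.84 that the trial was really sized for 80% power, or that the misprint contributes to the shortfall. The documents do not support either. The 10.51 reproduces only at 90%. Had 0.84 been used, the requirement would have been 8, and 15 enrolled would have more than covered it. Nor is there a planned step at which the wrong Z would be used to re-size a cohort: section 10.4.7 rules out interim analysis, and section 10.5 provides for no re-estimation.

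**Conclusion.** Both errors are real, independent of each other and minor.

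The loss allowance is one subject per cohort too small: 16 are needed where the plan states 15. If 10 subjects prove evaluable, power is 88.5% by the plan's formula, 1.5 points under the stated 90%. This takes as given the plan's effect size of 1.0, its normal approximation, and a 30% loss applied in full to the sizing endpoint. Sixteen meets the evaluable target in expectation; it does not guarantee 11 in every cohort.

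The printed 0.84 is a typographical error. It makes the table inconsistent but leaves 11 and 15 as they are.

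**What to change.** In section 10.5:

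1. Replace 0.84 with 1.28 on the 90% row. Using 1.282 would let a reader reproduce 10.51 by hand, since (1.96 + 1.282)² = 10.51; with 1.28 the hand result is 10.50. Either rounds up to 11.
2. Replace the 14.30 and 15 with 11 / (1 − 0.30) = 15.7, rounded up to 16, and change the concluding sentence to match. Alternatively, keep 15 and state that it covers a loss of 4 in 15, about 27%, and not 30%.

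The cost is an edit to the table and, if 16 is adopted, to its conclusion, with one more subject per cohort in the target. The ceilings of 50 and 25, the visits and the procedures do not change.
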